5.2.10. Analyses for Continuous and Qualitative Variables

Continuous variables will be summarized using descriptive statistics ie, number of non-missing values and number of missing values [ie, n (missing)], mean, median, Std Dev, minimum, maximum and first and third quartile (Q1 and Q3).

Qualitative variables will be summarized by frequency counts and percentages. Unless otherwise specified, the calculation of proportions will include the missing category. Therefore counts of missing observations will be included in the denominator and presented as a separate category.

In case the analysis refers only to certain visits, percentages will be based on the number of participants still present in the study at that visit, unless otherwise specified.

5.2.11. Analyses for Time-to-Event Endpoints

Time to event endpoint will be summarized using the Kaplan-Meier method and estimated survival curves will be displayed graphically if appropriate. The median event time (if appropriate) and 2-sided 95% CI for the median will be provided based on the Brookmeyer-Crowley method. In case the number of participants with PD after a confirmed CR or confirmed PR is small for the Kaplan-Meier method, descriptive statistics will be provided.

5.3. Methods to Manage Missing Data

Unless otherwise specified, all data will be evaluated as observed, and no imputation method for missing values will be used.

Any imputations will occur at the analysis dataset level. Additionally, in all data listings imputed values will be presented and flagged as imputed.

Missing statistics, eg, when they cannot be calculated, should be presented as 'ND' for not done, 'NR' for not reached or 'NA' for not applicable. For example, if N=1, the measure of variability cannot be computed and should be presented as 'ND' or 'NA'.

5.3.1. Missing ECG Data

For QTc analyses, no values will be imputed for missing data. If one or two of the triplicate measurements for an ECG parameter are missed, the average of the remaining two measurements or the single measurement can be used in the analyses. If all triplicate measurements are missing at baseline for an ECG parameter, no values will be imputed.

5.3.2. Handling of Incomplete or Missing Dates

5.3.2.1. Adverse Events

AE Onset Date:

The following imputation rules apply if the event is unique for a participant or it is the first of a series of similar events; otherwise, the AE Onset Date will not be imputed:

- If the AE Collection Date is not missing, is less than the Date of First Exposure to Treatment, and is less than the AE Stop Date, then AE Onset Date is set to the Date of AE Collection.
- If the Previous Visit Date is greater than the Date of First Exposure to Treatment and less than the AE Stop Date, the AE Onset Date is set to the previous visit date.
- If the Date of First Exposure to Treatment is greater than the previous visit date and less than the AE Stop Date, the AE Onset Date is set to the Date of First Exposure to Treatment.
- Otherwise AE Onset date is set to the AE Stop date.

AE Stop Date:

Ongoing events will have the AE Stop Date set to one of the following values:

- Date of Death, if the participant died and a date of death exists.
- Maximum of (Withdraw date, AE Onset Date, AE Collection Date) if the participant withdrew from the study and a date of withdraw exists.

- Maximum of (AE Onset Date, Subject Summary Collection Date, AE Collection Date) if the Subject Summary CRF page exists but a date of withdraw does not exists.
- Maximum of (Last Treatment Date, AE Onset Date) if no Subject Summary page exists.

Imputation will only occur if event is unique for the participant, or it is the last of a series of similar events; otherwise the Stop Date will not be imputed. Adverse Events are deemed similar if they have the same verbatim term.

Resolved events will have the AE Stop Date set to the maximum of the AE collection date and the AE Onset date.

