5.3. Administration

The product will be administered in accordance with the India LPD.

The recommended dosage of dacomitinib is 45 mg taken orally once a day at approximately the same time each day, until disease progression, participant refusal/lost to follow-up, or unacceptable toxicity occurs. Dacomitinib can be taken with or without food.

The participant should take dacomitinib the same time each day. If the participant vomits or misses a dose, he/she should not take an additional dose or make up a missed dose but continue with the next scheduled dose.

The dose of dacomitinib should be reduced for adverse reactions as described in Table 1. Dose modifications for specific adverse reactions are provided in Table 2.

Table 1. Dacomitinib Recommended Dose Reductions for Adverse Reactions

Dose level	Dose (Once a Day)
First dose reduction	30 mg
Second dose reduction	15 mg

Table 2. Dacomitinib Dose Modifications for Adverse Reactions

Adverse Reaction	Severity ^a	Dosage Modification
Interstitial lung disease	Any Grade	
Permanently discontinue dacomitinib.
Diarrhea	Grade 2	
Withhold dacomitinib until recovery to less than or equal to Grade 1; then resume dacomitinib at the same dose level.For recurrent Grade 2 diarrhea, withhold until recovery to less than or equal to Grade 1; then resume dacomitinib at a reduced dose.
	Grade 3 or 4	
Withhold dacomitinib until recovery to less than or equal to Grade 1; then resume dacomitinib at a reduced dose.
Dermatologic Adverse Reactions	Grade 2	
Withhold dacomitinib for persistent dermatologic adverse reactions; upon recovery to less than or equal to Grade 1, resume dacomitinib at the same dose level.For recurrent persistent Grade 2 dermatologic adverse reactions, withhold until recovery to less than or equal to Grade 1; then resume dacomitinib at a reduced dose.
	Grade 3 or 4	
Withhold dacomitinib until recovery to less than or equal to Grade 1; then resume dacomitinib at a reduced dose.
Other	Grade 3 or 4	
Withhold dacomitinib until recovery to less than or equal to Grade 2; then resume dacomitinib at a reduced dose.

^a NCI CTCAE Version 4.03.

If a participant cannot tolerate treatment after a dose reduction to 15 mg, treatment will be permanently discontinued.

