3. ENDPOINTS AND BASELINE VARIABLES: DEFINITIONS AND CONVENTIONS

3.1. Primary Endpoint

The primary endpoint is the incidence of AEs, defined as the number of participants with treatment-emergent adverse events (TEAEs) from the time of first dose to 28 days post last dosing date or the date prior to initiation of a new anticancer therapy, divided by the number of participants in the Safety Set (see [Section 4](#)).

An adverse event is considered treatment-emergent if any of the following apply:

- The event occurs on-treatment (defined in [Section 3.5](#)) and was not seen prior to the start of treatment.
- The event was seen prior to the start of treatment but increased in National Cancer Institute Common Terminology Criteria for Adverse Events (NCI CTCAE) v4.03 grade while on-treatment.

Treatment-emergent adverse events will be characterized by type, frequency, severity (as graded by the investigator according to NCI CTCAE version 4.03 and coded by the Sponsor using Medical Dictionary for Regulatory Activities [MedDRA]), timing, seriousness, and relationship to dacomitinib.

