5.3.2.5. Other Dates

Imputation methods for other partial dates as follows:

- If the day of the month is missing for a start date used in a calculation, the first day of the month will be used to replace the missing date.
- If both the day and month are missing, the first day of the year is used.
- For stop dates, the last day of the month, or last day of the year is used if the day or day and month are missing, respectively.
- If the date is completely missing, no imputation will be performed.

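### SAP 5.3.2.1 ignores a recorded onset month or year for adverse events and gives no treatment-emergent status to undated repeat episodes, so some events can be misclassified

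*SAP*

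**What the plan says.** SAP 5.3.2 is headed "Handling of Incomplete or Missing Dates", so 5.3.2.1 governs partial AE dates too. Imputation is restricted to an event that is unique or "it is the first of a series of similar events; otherwise, the AE Onset Date will not be imputed". Events are similar if they share a verbatim term. In order, the onset rules are:

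1. Collected before first dose and before the stop date: onset is the collection date.
2. Previous visit after first dose and before the stop date: onset is the previous visit.
3. "If the Date of First Exposure to Treatment is greater than the previous visit date and less than the AE Stop Date": onset is the first-dose date.
4. Otherwise: onset is the stop date.

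None refers to a recorded month or year. The neighbouring sections on last dose (5.3.2.2), death (5.3.2.3) and new anticancer therapy (5.3.2.4) do. So does 5.3.2.5, Other Dates: "If the day of the month is missing for a start date used in a calculation", the first of that month is used.

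SAP 3.1 calls an event treatment-emergent if it occurs on-treatment "and was not seen prior to the start of treatment", or if it was present before and rose in grade on-treatment. SAP 3.5 counts an AE on the day of first dose as on-treatment. SAP 6.1.1 bases its summaries on treatment-emergent events unless otherwise specified.

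**The concern.** TEAE incidence is the primary endpoint, and the onset date decides whether an event is a TEAE. Two things can go wrong.

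- **Pre-treatment symptoms.** If the record shows that a symptom began in a month before dosing, a rule that discards the month can place its onset on or after first dose. That adds a TEAE which the data contradict.
- **Repeat episodes.** If a later episode has an incomplete onset, nothing is imputed and nothing is said about its status. Someone must decide at programming stage, with the data in hand. The episode may carry the worst grade, the seriousness or the dose action. Protocol 5.3, Table 2, for example, links a dose reduction to a repeat episode: "For recurrent Grade 2 diarrhea, withhold until recovery to less than or equal to Grade 1", then resume at a reduced dose.

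The two errors run in opposite directions and affect different records, so they cannot be relied on to cancel.

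**Working it through.** **The plan's own figure.** Protocol 9.2 gives a maximum standard error of 0.05 for an AE rate with 100 participants. Check: sqrt(0.5 × 0.5 / 100) = 0.05. It is reproduced and not in dispute. It sets the scale: one misclassified participant moves a row by 1/100 = 0.01, or 0.2 of that standard error; five move it by 0.05, or one standard error.

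**The onset rules on constructed dates.** Assumed: first dose 10 Apr 2021, screening visit 25 Mar, Cycle 2 Day 1 on 8 May, Cycle 3 Day 1 on 5 Jun, recorded onset March 2021 with the day missing. The rules are applied literally and in order.

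| Case | Collected | Previous visit | Stop | Rule | Imputed onset |
|---|---|---|---|---|---|
| a | 25 Mar | 25 Mar | 1 May | 1 | 25 Mar, pre-treatment |
| b | 10 Apr | 25 Mar | 1 May | 3 | 10 Apr, on-treatment |
| c | 10 Apr | 25 Mar | 5 Apr | 4 | 5 Apr, pre-treatment |
| d | 8 May | 10 Apr | 1 May | 4 | 1 May, on-treatment |
| e | 5 Jun | 8 May | 1 Jul | 2 | 8 May, on-treatment |

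Four cases (a, b, d, e) stop after first dose. Three of them move to an on-treatment date although the record says March. The condition is first collection on or after first dose together with a stop after it.

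Case d shows a further gap. When the previous visit is the first-dose day, rules 2 and 3 both fail because each demands strict inequality, and onset falls to the stop date. For an ongoing event the stop date is itself imputed, in several branches from the onset date, which is circular. Suppose an event with a wholly missing onset is collected on 8 May 2021 and is still ongoing when the participant withdraws on 1 Feb 2022. Its onset becomes 1 Feb 2022. If the last dose was before 4 Jan 2022 (4 Jan + 28 days = 1 Feb), a first-cycle event lands outside the on-treatment window.

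**A repeat episode.** Take a first episode that is dated, on-treatment and Grade 1, and a second with the same verbatim term that is undated, Grade 3 and serious.

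| | Second kept | Second dropped |
|---|---|---|
| Any TEAE | yes | yes |
| Preferred Term count | 1 | 1 |
| Maximum grade | 3 | 1 |
| Serious | yes | no |

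**How often.** The documents give no rate of incomplete AE dates, so the following shares are assumptions that show only a range.

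- Pre-existing symptom first entered on or after Day 1 in 10–40% of participants, of which 5–30% have a pre-dose month only: 0.10 × 0.05 = 0.5 per 100 to 0.40 × 0.30 = 12 per 100. This makes no allowance for Protocol 8.2, which would lower it.
- Worst or dose-modifying event at a repeat episode in 10–40%, of which 2–10% have an incomplete onset: 0.10 × 0.02 = 0.2 per 100 to 0.40 × 0.10 = 4 per 100, and only if undated repeats are dropped.

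**The case against.** **Repeat episodes.** A reader might infer that recurrent events with incomplete dates fall out of the primary AE tables. The documents do not say so. Declining to impute leaves the recorded partial date in place, and SAP 5.3 has data evaluated as observed unless otherwise specified. An episode recorded in a month that lies wholly within dosing can be classed as on-treatment without a day. What stands is that the SAP sets no status, so either treatment is open.

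The reach is also limited. Only repeats with the same verbatim term and an incomplete or missing onset are involved. When the first episode is already a TEAE, the binary primary variable, SOC/PT incidence and the overall event count, which is unique by Preferred Term, do not change. Incidence could change if the first episode was pre-treatment and the undated repeat was of higher grade. Serious events are reported within 24 hours with detailed follow-up (Protocol 8.13.1), so their dates should be more complete. Dose reductions and interruptions are also summarized from dosing records (SAP 6.5.3.2), whatever the AE onset.

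**Pre-treatment symptoms.** A reader might also infer that known pre-treatment symptoms generally become TEAEs. Cases a and c show otherwise. Protocol 8.2 starts AE recording on the CRF only after a dose has been taken, and medical history is captured at Screening, although the Schedule of Activities also marks AEs at Screening. It can be argued that a recorded pre-dose month already fails the not-seen-before clause of SAP 3.1. That is a sensible reading, but the SAP does not say that the recorded month overrides the imputed date.

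**Other Dates.** Nor does 5.3.2.5 close the gap. It covers dates not handled elsewhere. Applied here, it would place any same-month onset before dosing whenever dosing began after the 1st, and it would conflict with the bar on imputing repeats.

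**Conclusion.** The concern holds in a limited form. Read literally, SAP 5.3.2.1 discards a recorded month or year and can turn an AE with a known pre-treatment month into a TEAE, provided it was first collected on or after first dose and stopped after it. For repeat episodes the defect is silence: no treatment-emergent status is given. Understatement of maximum-grade, seriousness and AE-action tables follows only if undated repeats are dropped.

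The any-AE proportion will hardly move. The exposure is in Preferred Term rows for pre-existing symptoms, and in the grade, seriousness and action rows for repeats, at 1 percentage point per participant. The number of participants is unknown; the per-100 ranges above rest wholly on assumed shares and are not estimates. The point is worth correcting because a stated rule can contradict recorded data on the primary endpoint and the correction is cheap. It does not threaten the main safety conclusion.

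**What to change.** Amend SAP 5.3.2.1 as follows.

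- **Partial onset.** Use the recorded month and year. A month earlier than that of first dose is pre-treatment. The same month is imputed as the first-dose date, unless the AE stopped before first dose, in which case it is pre-treatment. A later month is imputed as the first of that month. Apply the same logic when only the year is known. No imputed onset may fall after the AE stop date.
- **Completely missing onset.** Keep the previous-visit rules for this case only. In the second rule, change greater than to greater than or equal to, so that an event whose previous visit was the first-dose day does not default to its stop date.
- **Repeat episodes.** Apply the rules to them as well, with onset no earlier than the start of the preceding episode.
- **Default.** State that an event whose onset still cannot be placed, and that is not known to have stopped before first dose, is treatment-emergent.

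The stop-date exception matters. With onset July 2021, stop 10 Jul and first dose 15 Jul, imputing the first-dose date would create a false TEAE that the present fallback rule avoids.

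Under this wording all five March cases are pre-treatment. The cost is SAP text and a small change to the AE dataset derivation, with no new data collection. The downside is that a few undated repeat events will be counted as treatment-emergent by default.

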8. ADVERSE EVENT REPORTING

8.1. Adverse Events

All observed or volunteered AEs regardless of treatment group or suspected causal relationship to the investigational product(s) will be reported as described in the following sections.

For all AEs, the investigator must pursue and obtain information adequate both to determine the outcome of the AE and to assess whether it meets the criteria for classification as an SAE requiring immediate notification to Pfizer or its designated representative. For all AEs, sufficient information should be obtained by the investigator to determine the causality of the AE. The investigator is required to assess causality. Follow-up by the investigator may be required until the event or its sequelae resolve or stabilize at a level acceptable to the investigator, and Pfizer concurs with that assessment.

As part of ongoing safety reviews conducted by the Sponsor, any nonserious AE that is determined by the Sponsor to be serious will be reported by the Sponsor as an SAE. To assist in the determination of case seriousness, further information may be requested from the investigator to provide clarity and understanding of the event in the context of the clinical study.

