2.1.1. Primary Estimand

The primary estimand is the incidence of adverse events from the time of first dose to 28 days post last dosing date or the date prior to initiation of a new anticancer therapy, whichever occurs first for all participants who receive at least one dose of dacitinib, regardless of dosing interruptions or dosing compliance. It includes the following 4 attributes:

- Population: Participants with metastatic Non-Small Cell Lung Cancer (NSCLC) with EGFR exon 19 deletion or exon 21 L858R substitution mutations as defined by the inclusion and exclusion criteria, and who receive at least one dose of dacitinib;
- Variable: Binary indicator of whether any AE occurred at least once;
- Intercurrent event(s): All data after the intercurrent event “initiation of a new anticancer therapy (-1 day)” or “treatment discontinuation (+28 days post last dosing date)” will be excluded. Dosing interruptions or dosing compliance are not considered as intercurrent event for this analysis;
- Population-level summary: Incidence of AEs defined as the number of participants with AEs from the time of first dose to 28 days post last dosing date or the date prior to initiation of a new anticancer therapy, divided by the number of participants in the Population.

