3.5. Safety Endpoints

Safety endpoints will be summarized based on the on-treatment period unless otherwise specified.

On-treatment is defined as the time from the first dose of study treatment through end of study follow-up (ie, 28 days after last dose) or the date prior to initiation of a new anticancer therapy, whichever occurs first. The start of new anticancer therapy after the first dose of study treatment is derived as outlined in [Section 5.2.3](#). Adverse events occurring on the same day as the first dose of study treatment will be considered to have occurred during the on-treatment period. All other assessments which occur on the same day as the first dose of study treatment will be considered baseline assessments (see [Section 3.4](#) for baseline definition).

Safety data collected outside the on-treatment period will be listed but not summarized.

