5.2.2. Definition of Cycle and Cycle Day

Cycle start and end dates are derived per participant. Treatment will be dispensed at the beginning of every 28-day cycle.

- For Cycle X, the actual cycle start date for each participant is:
 - The earliest start date of dosing (dose>0 at that visit) in Cycle X visit case report form (CRF) exposure page.

- For all but the last cycle.
 - Actual cycle stop date is calculated as the start date of the next cycle minus one day.
 - Actual cycle duration is calculated from Day 1 of a cycle to the day prior to Day 1 of the next cycle, as follows:

$$\text{Actual Cycle Duration (weeks)} = (\text{cycle stop date} - \text{cycle start date} + 1)/7.$$

- For the last cycle, actual cycle duration is calculated as follows:
 - $\text{Actual Cycle Duration (weeks)} = (\text{last date of study treatment} - \text{cycle start date} + 1)/7.$

The cycle day will be calculated as:

$$\text{Cycle day} = \text{Date of the assessment/event} - \text{cycle start date} + 1.$$

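### Two date-imputation gaps: an undated AE takes its stop date as onset when the previous visit is the first-dose day, and a known last-dose month is overwritten when its year is earlier

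*SAP*

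**What the plan says.** SAP 5.3.2.1 imputes AE onset when the event is unique for the participant or the first of a similar series. In order:

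1. AE collected before first dose and before its stop date: onset is the collection date.
2. "If the Previous Visit Date is greater than the Date of First Exposure to Treatment and less than the AE Stop Date": onset is the previous visit.
3. "If the Date of First Exposure to Treatment is greater than the previous visit date and less than the AE Stop Date": onset is the first-dose date.
4. "Otherwise AE Onset date is set to the AE Stop date".

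The SAP does not define the previous visit date. For ongoing events the same section fills in the stop date. Its first branch is "Date of Death, if the participant died and a date of death exists"; the other three take a maximum that includes the AE onset date. No order is given between imputing onset and imputing stop.

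On timing, SAP 5.2.2 says "Treatment will be dispensed at the beginning of every 28-day cycle" and starts each cycle at its first non-zero dose. The protocol's Schedule of Activities puts visits on Day 1 of each cycle, with AEs recorded at each visit. SAP 3.5 ends the on-treatment period 28 days after last dose, or the day before new anticancer therapy if that is earlier, and adds: "Safety data collected outside the on-treatment period will be listed but not summarized". The primary estimand (SAP 2.1.1) uses "Variable: Binary indicator of whether any AE occurred at least once".

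For a partial last-dose date with an end-of-treatment (EOT) page or a death date, SAP 5.3.2.2 has three outcomes. Only the year known, and earlier than the EOT/death year: 31 December of that year. Year and month known, same year, earlier month: last day of that month. Everything else: the earlier of EOT and death. SAP 5.3.2.4, on new anticancer therapy, has a separate branch for a known month in an earlier year and keeps that month.

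**The concern.** The second and third onset rules are both strict, so a previous visit on the first-dose date satisfies neither. The event goes to the catch-all and its onset becomes its stop date. For an AE first collected at Cycle 2 Day 1, the scheduled visit before it is Cycle 1 Day 1, the day dosing starts, so the tie is the natural case for an undated Cycle 1 AE. A one-day shift in the previous visit then changes the imputed onset greatly, with no rationale given.

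At stake are the onset and duration shown in the AE listings, which Protocol 9.6.1 says will include duration. In a narrower set of cases the event also drops out of the treatment-emergent (TEAE) tables. Late stop dates are possible, because Protocol 8.1 says "Follow-up by the investigator may be required until the event or its sequelae resolve or stabilize".

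The last-dose gap contradicts recorded data: a known month and year are replaced by a date in a later year. The imputed last dose sets the 28-day safety window, treatment duration and dose intensity. It also enters the imputation of new-therapy start dates and of some AE stop dates.

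**Working it through.** No figure in the plan depends on these rules, so there is nothing to reproduce. The check applies each rule literally. All dates are illustrative.

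**AE onset: where the gap lies.** Take an AE collected on or after first dose, with a stop date after both first dose and the previous visit. Rule 1 cannot apply. A previous visit after first dose meets rule 2; one before first dose meets rule 3; one equal to first dose meets neither. Running the rules over collection days 0 to 59, previous visits from 28 days before to 59 days after first dose, and stop days 1 to 59 (all counted from first dose) gave the same answer: only offset 0 reaches the catch-all.

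**AE onset: consequences.** First dose = Cycle 1 Day 1 visit = Day 1; AE with missing onset collected on Day 29; last dose Day 270. The window ends on Day 270 + 28 = Day 298, or on Day 284 if new therapy starts on Day 285.

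| Case | Stop date used | Window ends | Onset as written | In TEAE tables? |
|---|---|---|---|---|
| Resolved, stop recorded Day 25 | 25 | 298 | Day 25 | yes |
| Stop recorded Day 310 | 310 | 298 | Day 310 | no |
| Ongoing, death Day 330 | 330 | 298 | Day 330 | no |
| Ongoing, death Day 290 | 290 | 298 | Day 290 | yes |
| Ongoing, new therapy Day 285, withdrawal Day 290 | 290 | 284 | Day 290 | no |
| Ongoing, no Subject Summary page | 270 | 298 | Day 270 | yes |

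The four ongoing cases assume that the stop date is imputed first and onset is then taken from it. The two recorded-stop cases need no such assumption.

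With the previous visit on the day before dosing, all six give onset Day 1; with it on Day 2, all six give Day 2. All are then treatment-emergent. With greater-than-or-equal in rule 2 and the tie kept, all six give Day 1 and all are treatment-emergent. (For the ongoing cases this uses the same stop dates.)

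In the first case the listed duration is 25 − 25 + 1 = 1 day as written, against 25 − 1 + 1 = 25 days with onset at Day 1.

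A participant whose only event of a given type is lost changes that rate by 1/100 = 1 percentage point. The any-AE rate changes only if the participant has no other TEAE.

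**Last dose.** SAP 6.5.3.1 gives duration = (last − first + 1)/7 weeks, dose intensity = cumulative dose/duration, and relative dose intensity (RDI) = 100 × dose intensity/(7 × d). Assume d = 45 mg and full planned dosing to the end of the known month, so that RDI is 100% when the month is kept. RDI as written is then the ratio of the two durations.

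| | First dose | Recorded last dose | EOT | As written | Month kept | Difference | Duration, kept vs written | RDI as written |
|---|---|---|---|---|---|---|---|---|
| A | 01 Jul 2020 | Dec 2020 | 05 Jan 2021 | 05 Jan 2021 | 31 Dec 2020 | 5 days | 184 vs 189 days (26.3 vs 27.0 weeks) | 184/189 = 97.4% |
| B (wide gap) | 01 Mar 2021 | Nov 2021 | 10 Feb 2022 | 10 Feb 2022 | 30 Nov 2021 | 72 days | 275 vs 347 days (39.3 vs 49.6 weeks) | 275/347 = 79.3% |

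Two comparisons locate the fault. January 2022 with EOT 10 February 2022 (same year) gives 31 January 2022, as it should. If only the year 2020 were recorded in case A, the first sub-rule would return 31 December 2020. Recording the month as well therefore gives a worse answer than omitting it.

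**The case against.** The strongest reply accepts both gaps and disputes their importance.

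- *The text never says that imputed onset alone decides treatment-emergence.* SAP 3.1 speaks of the event occurring on-treatment, SAP 3.5 excludes data collected outside the window, and every example AE is collected inside it, on Day 29. The protocol's definition of treatment-emergent has no upper limit. This is fair as a statement of what the loss depends on. Dating an event by its onset is still the natural reading of SAP 3.1 and 3.5.
- *Resolved events have their own stop rule*, the later of collection and onset. Where the stop date is missing, this generally keeps it near collection and limits the harm. In a section on missing dates it does not displace a recorded stop such as Day 310.
- *The true onset is unknown.* Correct: 25 days is the longest treatment-emergent duration for that event, not its known duration. The fault is that the imputation jumps to the other extreme on a tie and nowhere nearby.
- *The harmful cases are unusual.* Onset must be missing, an unscheduled visit or a first dose after the visit date breaks the tie, and most affected AEs stay in the tables. Imputed values are flagged (SAP 5.3), and the SAP has no summary of AE duration or time to onset. All of this stands.
- *The 72-day example is remote*, given 28-day visits with tablet counts. This also stands; the 5-day case is the realistic one. A last dose set too late widens the AE window, so it does not undercount AEs.

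These points limit the size of the problem. None supplies the missing branch in either rule.

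**Conclusion.** Both rules are wrong as written; the severity is minor. Strictly, the tie is not undefined: it has no rule of its own, and the catch-all gives it an unsuitable date. Confidence in the two gaps is high, since they follow from the wording alone.

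The AE gap mainly misstates onset and duration in the listings. An event leaves the TEAE tables only if its actual or imputed stop date is more than 28 days after last dose, or on or after the start of new therapy. That conclusion assumes that treatment-emergence is dated by onset and that the previous visit is the one before collection. For ongoing events it also assumes that the stop date is imputed before onset.

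The last-dose gap adds about 5 days and costs 2.6 points of RDI (100 − 97.4) for one participant in the realistic example. The number of affected records cannot be derived from the documents and is probably low. The study tests no hypothesis, and no stated figure changes.

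**What to change.** Two edits repair the faults:

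- **SAP 5.3.2.1, second onset rule:** require the previous visit to be on or after the first-dose date, instead of strictly after it.
- **SAP 5.3.2.2, month-known rule:** extend the condition so that the last day of the known month is also returned when the recorded year is earlier than the year of min(EOT, death). This matches SAP 5.3.2.4.

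Three clarifications in 5.3.2.1 should go with them: define the previous visit date; state that for an ongoing event onset is imputed before the stop date, with the before-stop condition treated as met; and keep an imputed onset within any month or year that was recorded.

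The cost is a few words in two SAP subsections and the matching program lines. No new data are needed.
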